## 2 SCHEDULE OF ASSESSMENTS

	Screening and enrollment	C1	C2	C3	C4	C5 1	C6 1	C7 1	C8 1	T	H1	H2	H3	H4	H5	H6	H7	H8	Withdrawal
Week	-2 to 0	C1	C2	C3	C4	C5	C6	C7	C8	T	H1	H2	H3	H4	H5	H6	H7	H8	
C=in clinic    T=transition at home with trained dialysis professional present    H=at home																			
Informed consent, demographics	x																		
Inclusion and exclusion criteria	x																		
Medical and surgical history 	x																		
Disease history	x																		
Dialysis treatment history	x																		
Pregnancy Test 	x																		
Device training		x	x	x	x	x	x	x	x										x
Physical examination		x																	x
Vital signs		x	x	x	x	x	x	x	x	x	x	x	x	x	x	x	x	x	
Biochemistry, hematology 		x	x		x		x		x		x	x	x	x	x	x	x	x	
Treatment adequacy 		x	x	x	x	x	x	x	x	x	x	x	x	x	x	x	x	x	
Preparation of home setting						during this period													
Training on software						during this period													
RO water/dialysate quality 						x				x	x				x			x	x
Treatment with Quanta SC 		x	x	x	x	x	x	x	x	x	x	x	x	x	x	x	x	x	
Device deficiency assessment		x	x	x	x	x	x	x	x	x	x	x	x	x	x	x	x	x	
Treatment flowsheet										x	x	x	x	x	x	x	x	x	
Usability 										x	x	x	x	x	x	x	x	x	
Time to recovery after dialysis (TTR) 		x								x		x					x	x	
EQ-5D-5L 		x								x							x	x	
MOS Sleep Index 		x								x							x	x	
Zarit Burden Interview (ZBI12) 																	x	x	
Renal Treatment Satisfaction Questionnaire		x								x							x	x	
Edmonton Symptom Assessment Scale (ESAS-r) 		x								x							x	x	
Upload Clinical utility Report 																	x	x	
Reliability 										monitored continuously during this period									
Proportion of participants and caregivers successfully trained						x	x	x	x										
Adverse Events										collected continuously during this period									
Concomitant Medications 	x									collected continuously during this period									
Reason for withdrawal																		x	
Review of HCP support & interactions 										x	x	x	x	x	x	x	x	x	

 Visits C1–C4 will occur for all participants. Visits C5 through C8 will occur, week-by-week, if training competence has not yet been demonstrated. Once training competence is demonstrated, remaining clinic (C)

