visits will be skipped and visits T and H1–H8 will begin.

 including comorbidities profile

 to be performed in female of childbearing potential

 Participant can draw their own blood during visits T and H1–H8. Blood will be analyzed for sodium (Na), urea (BUN), potassium (K), creatinine (Cr), bicarbonate (HCO3), magnesium (Mg), phosphate (Phos), chloride (Cl), calcium (Ca), albumin (Alb), iron (Fe), transferrin saturation (TS), total protein (TP), ferritin (Fn), alkaline phosphatase (ALP), parathyroid hormone (PTH), total iron binding capacity (TIBC), aspartate transaminase (AST), alanine aminotransferase (ALT), hemoglobin (Hb), hematocrit (Hct), white cell count (WBC), platelet count (PC), reticulocyte count (RC). BUN is collected immediately before and after Quanta SC+ treatment

 Kt/V done mid-week every week. In home setting, participants may be instructed on how to draw their own blood sample or bloodwork can be drawn by trained research staff.

 During device installation in-center and in-home and monthly thereafter, water/dialysate samples will be collected and tested

 Dialysis prescription is 3 times per week, 4 hours per session or facility standard for C1 through C4 and also C5 through C8 if required; 4 times per week, 3.5 hours per session for T and H1 through H8. Clinic visits will be Monday, Wednesday, and Friday (unless otherwise approved by Sponsor). In home visits will be Monday, Wednesday, Friday, and Saturday (unless otherwise approved by Sponsor).

 Participants queried: required assistance with any aspect of treatment over the prior 7 days and if so, with which of the following tasks: machine set up, clearing of alarms, machine take down, fistula/needling or catheter connection

 TTR is completed once after a dialysis treatment during the week of C1 – H1 – H4 and H8 or at withdrawal; not all treatments within those weeks ([Lindsay 2006](#))

 Collected twice: (1) prior to first home treatment, and (2) if there have been any home treatments, then during last home treatment or withdrawal.

 Collected prior to first in-clinic treatment, prior to first in home treatment, prior to H5 treatment, and after last in-home treatment. Also collected prior to C5 treatment if competency training not achieved by treatment C4.

 Caregiver—not participant—completes ZBI. ([ZBI12, Bédard 2001](#))

[figure not shown]

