## 6.5 Study Structure

Following enrollment participants will begin hemodialysis treatments on the SC+ machine on a prescription of four-hour treatments, three times per week or per facility standard for a baseline period of 4 weeks within a hemodialysis facility administered by qualified dialysis clinical staff. During this time, both patients and caregivers will undergo extensive training and competency sign off. Competency, defined as three observed treatments without intervention or request for intervention from either the participant or their caregivers, will be assessed to ensure they are safe and proficient to conduct regular treatments in the home setting. This 4 week period can be extended week by week to a maximum of 8 weeks until competency sign off is achieved. If competency signoff is not achieved after 8 weeks, the participant will be withdrawn from the study. Following this in-clinic phase, a one-week transition phase of home hemodialysis will be provided with a dialysis professional present, followed by the home hemodialysis phase (test phase) without a dialysis professional present for an additional 8 weeks. Treatments in the transition and home hemodialysis phases will be performed by the participant and caregiver, 4 times per week, 3.5 hours each treatment.

Participants will undergo standardized physical examinations by a physician at the beginning of the in-clinic treatment phase (C1) and at the end of the self-care phase (H8) and at withdrawal. Regular physical exams, biochemistry, and hematology testing will be performed as defined below.

The study will be considered complete with regard to the primary objective after the minimum evaluable participants have completed the protocol and associated procedures defined below.

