6 ANALYSIS POPULATIONS

6.1 FULL ANALYSIS SET (FAS)

The full analysis set (FAS) for this study will include all participants who are enrolled in the study. A sensitivity analysis performed on the FAS population with missing value imputation.

Subjects are considered enrolled in the trial after they have signed the informed consent form, met all of the inclusion criteria and none of the exclusion criteria, and who start the first study treatment during the first treatment period.

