7.3 METHODS FOR WITHDRAWALS AND MISSING DATA

Participants are free to withdraw at any time. A participant will be automatically withdrawn if training competency is not achieved after 8 weeks of in-clinic treatment (unless otherwise approved by the sponsor) or if treatments cease with SC+ for a period of more than 7 consecutive days during the course of the study or if 8 or more non-consecutive treatments are missed. Data taken prior to withdrawal will be used for study analysis.

All practical monitoring and follow-up steps will be taken to ensure complete and accurate data collection. However, it is expected that some data may be missing for the primary effectiveness endpoint, Kt/V, in the FAS population. Participants who are missing any Kt/V measurements during the in-center or in-home phases will be considered as “missing data participants” for the primary effectiveness endpoint. As a sensitivity analysis, missing data for the primary effectiveness endpoint will be imputed. The following imputation techniques will be conducted:

- Multiple Imputation (MI) using a fully conditional specification (FCS) method, in which a linear regression model including dry weight for a given week and all previous weekly Kt/V values for a given study phase (in-center or in-home) will be used in order to predict the primary effectiveness endpoint, Kt/V. Kt/V will be imputed for each week for a given study phase. There will be no imputation of missing Kt/V during the transition phase. To be explicit, imputation will occur in the following manner:
 - In-Clinic Weeks
 - Kt/V for C1 will be imputed using only dry weight at C1
 - Kt/V for C2 will be imputed using dry weight at C2 and Kt/V at C1
 - Kt/V for C3 will be imputed using dry weight at C3 and Kt/V at C1 and C2
 - Kt/V for C4 will be imputed using dry weight at C4 and Kt/V at C1 through C3
 - Kt/V for C5 will be imputed using dry weight at C5 and Kt/V at C1 through C4
 - Kt/V for C6 will be imputed using dry weight at C6 and Kt/V at C1 through C5
 - Kt/V for C7 will be imputed using dry weight at C7 and Kt/V at C1 through C6
 - Kt/V for C8 will be imputed using dry weight at C8 and Kt/V at C1 through C7
 - In-Home Weeks
 - Kt/V for H1 will be imputed using only dry weight at H1
 - Kt/V for H2 will be imputed using dry weight at H2 and Kt/V at H1
 - Kt/V for H3 will be imputed using dry weight at H3 and Kt/V at H1 and H2
 - Kt/V for H4 will be imputed using dry weight at H4 and Kt/V at H1 through H3

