 - Kt/V for H5 will be imputed using dry weight at H5 and Kt/V at H1 through H4
 - Kt/V for H6 will be imputed using dry weight at H6 and Kt/V at H1 through H5
 - Kt/V for H7 will be imputed using dry weight at H7 and Kt/V at H1 through H6
 - Kt/V for H8 will be imputed using dry weight at H8 and Kt/V at H1 through H7

The number of imputations will depend on the fraction of missing information (FMI). Initially, a total of 50 imputations will be carried out to create 50 “complete” datasets, which has been demonstrated to produce stable estimates. If the highest FMI percentage is greater than 50, the number of imputations used will be increased to be equal to the highest FMI percentage. The repeated measures analysis of variance (ANOVA) containing terms for participant, treatment phase, and time points (weeks) and using an AR(1) covariance structure will be run on each of the 50 imputed data sets in order to obtain least squares mean (and its standard error) for the respective treatment period. Results will be combined across the datasets using standard multiple imputation theory to obtain a single point estimate, 95% confidence interval, and p-value for each of the treatment phases.

The primary efficacy analysis will initially be done on the evaluable population with no missing value imputation and will also be repeated on the PP population with no missing value imputation and on the FAS with missing value imputation as described above.

There will be no imputation for the primary safety endpoint or any secondary endpoints.

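### The SAP's imputation of home Kt/V ignores the participant's own clinic Kt/V, so the FAS sensitivity analysis treats anyone who never reached home as a typical home-reacher (minor)

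*SAP*

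**What the plan says.** SAP 7.3 plans multiple imputation by a chain of linear regressions and lists every model. The predictors are that week's dry weight and the earlier Kt/V values of the same phase. The home list opens with "Kt/V for H1 will be imputed using only dry weight at H1" and ends with "Kt/V for H8 will be imputed using dry weight at H8 and Kt/V at H1 through H7". No home model contains a clinic value. The clinic list runs in the same way to C8, for example "Kt/V for C5 will be imputed using dry weight at C5 and Kt/V at C1 through C4". On scope it says "Kt/V will be imputed for each week for a given study phase. There will be no imputation of missing Kt/V during the transition phase".

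The FAS (SAP 6.1) takes in enrolled participants "who start the first study treatment during the first treatment period", so reaching home is not required. Protocol 6.5 states: "If competency signoff is not achieved after 8 weeks, the participant will be withdrawn from the study". SAP 7.3 and 7.7 allow exceptions approved by the sponsor. SAP 13 itself notes that the FAS does not guarantee data in both phases.

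Protocol Section 2, footnote 1, says that visits C1 to C4 "will occur for all participants. Visits C5 through C8 will occur, week-by-week, if training competence has not yet been demonstrated". Once competence is shown, the remaining clinic "visits will be skipped and visits T and" the eight home weeks begin.

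**The concern.** Some FAS participants may have several clinic Kt/V values and no home value. For them the stated chain starts from dry weight alone at H1, and each later week builds on the values just imputed. The result is what a home-reacher of that dry weight would be expected to have. A low clinic Kt/V cannot pull it down, although Kt/V is scheduled weekly in the clinic. Participants who leave during the home phase keep their observed home values and are less affected.

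What is at stake is whether the sensitivity analysis can do its job. The SAP's primary population requires 75% of treatments completed (6.2), and the per-protocol population carries the same condition (6.3). Among the effectiveness analyses listed in SAP 9.1, the imputed FAS analysis is the only one that includes participants outside the evaluable population. It exists to show whether leaving them out matters.

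A practical gap goes with this. Someone who left before home has no dry weight at H1 to H8, and 7.3 does not say what to use instead.

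**Working it through.** **Inputs from the documents** (SAP 4, Protocol 10.2.1): mean Kt/V 2.5, threshold 2.1, SD 0.7, AR(1) with rho 0.5, one-sided alpha 0.025, n = 11 with eight weekly values.

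**The plan's own figure.** The 8 x 8 AR(1) matrix sums to 20.016. The SD of a participant's eight-week mean is sqrt(0.49 x 20.016/64) = 0.3915. Then n = (0.3915 x (1.960 + 1.282)/0.4)^2 = 10.06, rounded up to 11, with power 92.4% by the normal approximation. The stated n = 11 reproduces and does not depend on this point.

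**Assumed, because the documents do not give it:** the share of the FAS with no home Kt/V (5% to 20%), and how far those leavers' clinic Kt/V lies below that of the others (0.4).

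**Formula.** Bias in the imputed home mean = share x clinic deficit x slope. The slope is the expected drop in mean home Kt/V per unit drop across all clinic weeks.

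**Slopes.** Number the weeks C1-C4 = 1-4, T = 5, H1-H8 = 6-13.
- AR(1), rho 0.5: only the last clinic week matters. It is two weeks before H1, so the slope at H1 is 0.5^2 = 0.25. Averaged over eight home weeks: 0.25 x (1 - 0.5^8)/0.5/8 = 0.0623.
- Exchangeable 0.5 (assumed): 0.5/((1 + 3 x 0.5)/4) = 0.8.
- In between (assumed; correlation 0.25 + 0.75 x (1/3)^lag, which is 0.5 at lag 1): average 0.466.

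| Structure | 5% share | 20% share | Share of the 0.4 distance |
|---|---|---|---|
| AR(1) 0.5 (plan) | 0.05 x 0.4 x 0.0623 = 0.0012 | 0.20 x 0.4 x 0.0623 = 0.0050 | 0.3% to 1.2% |
| In between | 0.05 x 0.4 x 0.466 = 0.009 | 0.20 x 0.4 x 0.466 = 0.037 | 2% to 9% |
| Exchangeable 0.5 | 0.05 x 0.4 x 0.8 = 0.016 | 0.20 x 0.4 x 0.8 = 0.064 | 4% to 16% |

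**Does adding clinic Kt/V remove it?** Simulation: 50 participants, 20% leaving after C4 with a clinic mean 0.4 lower, dry weight constant and unrelated to Kt/V, 10 imputations, 1,500 runs, Rubin's rules on participant means as a simplification of the repeated measures model, Monte Carlo SE about 0.002. The stated models gave a bias of 0.006 (AR(1)), 0.039 (in between) and 0.065 (exchangeable). With the clinic mean added it was about 0.002 in all three. The SE hardly changed: 0.064 to 0.066, 0.074 to 0.074, and 0.085 to 0.080.

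Results vary with how leavers are chosen. In a second set of runs, 15% left, leaving became likelier as clinic Kt/V fell, and the deficit was not fixed at 0.4. Cross-phase correlations of 0, 0.25, 0.5 and 0.7 gave biases of about 0, 0.03 to 0.04, 0.06, and 0.07 to 0.08. All were within about 0.01 of zero once the clinic mean was added.

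**Which clinic weeks.** A participant who fails sign-off may attend C1 to C8. If only C1-C4 were used, C4 would sit six weeks before the H1 they would have had. The AR(1) slope at H1 would be 0.5^6 = 0.0156, averaging 0.0156 x (1 - 0.5^8)/0.5/8 = 0.004 instead of 0.062. Almost all the information would be lost. The last attended clinic week is always two weeks before H1, so including it restores 0.25 at H1.

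**The case against.** The strongest objection is size. Under the correlation that the plan states, the bias is at most 0.005 in the illustration, which nobody would notice. In the first simulation at 10% leavers the AR(1) result moved from 0.001 to -0.002, which is not a demonstrable gain. The larger figures need correlation structures that the sample-size section does not state. That stands, with one qualification: the analysis model has a participant term as well as AR(1), so some lasting difference between participants is not foreign to the plan.

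The deficit and the share also have no source, and the documents do not link sign-off to Kt/V. The 20% share is already slightly above the attrition named in SAP 4: 15% of 50 is 7.5, plus 2 deaths or transplants, gives 9.5/50 = 19%, and those 2 events are expected during the home phase. This stands as well.

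Four stronger readings are tempting and are not supported:
- A reader might infer that clinic weeks C5 to C8, skipped by design, will be imputed for everyone. SAP 7.3 exempts only the transition week, but Protocol Section 2 footnote 1 and SAP 7.7 make those weeks conditional on competence still being outstanding. Models for C5 to C8 have to be listed because some participants stay. A clarifying sentence is enough.
- A reader might infer that the imputation cannot be run without home dry weights. The SAP is silent, but a weight could be carried forward or itself imputed. It is a gap an analyst would fill, not an impossibility.
- A reader might infer that no other effectiveness analysis covers the FAS. That is true of the list in SAP 9.1. Protocol 10.4.1 also lists the FAS without imputation, and SAP 13 changes the primary population without saying that this analysis is dropped. Its status is arguable.
- A reader might take all 17 of 50 participants allowed to be non-evaluable (34%) as having no home Kt/V. The second set of runs then reaches 0.19 at a correlation of 0.7. But the 50-to-33 allowance concerns evaluability, not absence of home data.

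**Conclusion.** The point holds as a minor one. The text is clear: no home imputation model uses clinic Kt/V, so a FAS participant with no home value is imputed without regard to how they did in the clinic. Confidence in that is high.

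The consequence is conditional. The bias is upward only if low clinic Kt/V predicts leaving and Kt/V is correlated across phases, and it is zero if leaving is unrelated to clinic Kt/V. With the assumed 5% to 20% share and 0.4 deficit it runs from 0.001-0.005 under the plan's AR(1) 0.5 to 0.016-0.064 under an assumed exchangeable 0.5.

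The documents do not support a claim that the trial's conclusion is at risk. Success rests on the evaluable population without imputation. Even at the simulated bias of 0.065 with an SE of 0.085, the planned mean lies (2.5 - 2.1)/0.085 = 4.7 SE above the threshold. The case for change is that the data are already collected and the better model costs almost nothing.

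**What to change.** In SAP 7.3:
1. Add to every home-week model a summary of the participant's own clinic Kt/V over all clinic weeks attended, including C5 to C8 where attended. The mean of those weeks would do; the mean plus the last clinic value is better if correlation fades over time. With the mean, the largest model (H8) has 1 + 1 + 1 + 7 = 10 coefficients, leaving 23 residual degrees of freedom if 33 participants have an observed H8.
2. Where a week's dry weight is absent, use the last recorded dry weight. SAP 12.1.4 already relies on dry weight at C1, so a value should exist for FAS participants.
3. As a clarification only, state that clinic weeks skipped after sign-off are not missing and are not imputed, in line with Protocol Section 2 footnote 1 and SAP 7.7.

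No separate model for C5 to C8 is needed. The cost is SAP wording and imputation code, with no extra data, visits or participants.

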7.4 PROTOCOL DEVIATIONS

Protocol deviations will be summarized in the CSR. This summary will include the number and percent of participants (overall and by site) with each deviation type. Deviations will be classified as major or minor prior to database lock to determine which patients should be excluded from the PP population. Major protocol deviations are those that affects the soundness of the study data. A data listing of protocol deviations will also be generated.

7.5 MULTIPLE COMPARISONS AND MULTIPLICITY

For the trial to be considered a success, the null hypothesis must be rejected for both co-primary effectiveness endpoints, as well as for the primary safety endpoint. The co-primary effectiveness endpoints will each be tested at the one-sided $\alpha=0.025$ level of significance, where the one-sided alternative hypothesis represents a mean standardized weekly Kt/V of greater than or equal to 2.1, for both the in-clinic and in-home phases of the study, respectively. The primary safety endpoint will also be tested at the one-sided $\alpha=0.025$ level of significance, where the one-sided alternative hypothesis represents non-inferiority of the in-home adverse event rate to the in-clinic adverse event rate, under a non-inferiority margin of 10%. No adjustments for multiple comparisons will be made for the primary endpoints.

All secondary effectiveness and safety endpoints will be descriptive in nature and 95% confidence intervals will be presented. No adjustments for multiplicity will be made.

7.6 ASSESSMENT OF HOMOGENEITY

A test of homogeneity across sites will be done to determine if the study sites have reasonably homogeneous responses of the primary effectiveness endpoint (weekly standardized Kt/V) on the evaluable population. This will be performed using a one-way analysis of variance (ANOVA) for continuous outcomes with site as the independent variable, tested at a 0.15 level of significance. If the responses are not homogenous, the appropriate regression analysis will be done to determine if the lack of homogeneity is due to the site or due to a possible imbalance in baseline characteristics of the subjects across study sites. If the site effect is no longer significant at a 0.15 level of significance after adding the potentially unbalanced baseline covariates, then site will not be considered a source of lack of homogeneity.

The assessment of homogeneity will occur using available data only, and no imputation for missing primary endpoint data will occur.

7.7 TIMING OF ASSESSMENTS AND EVENTS FOR ANALYSIS

Patients will be considered enrolled in the study once they or their authorized representative have provided written informed consent and they have been documented to have successfully met all inclusion criteria and no exclusion criteria. In-clinic dialysis should start within 2 weeks of enrollment. Dialysis prescription during the in-clinic phase is 3 times per week, 4 hours per session. The in-clinic phase spans C1 through C4 at a minimum and continues for C5 through C8 until training competency is

established. Clinic visits will occur Monday, Wednesday, and Friday and blood sampling will be performed on Wednesday unless otherwise approved by sponsor. The start of the transition phase will begin the week after competency sign-off and the in-home phase will begin the following week. Dialysis prescription during the transition and in-home phases is 4 times per week, 3.5 hours per session. In-home visits will occur Monday, Wednesday, Friday, and Saturday unless otherwise approved by Sponsor. A participant will be automatically withdrawn if training competency is not achieved by C8, unless otherwise pre-approved by sponsor, or if treatments with SC+ cease for a period of more than 7 consecutive days during the course of the study or if 8 or more (non-consecutive) treatments are missed. Data taken prior to withdrawal will be included in study analyses.

C1 will be considered baseline for standard weekly Kt/V, as well as for biochemistry and hematology labs.

The baseline values for vital signs are the pre-dialysis measurements taken during the first treatment of C1.

